4.6.2 Major Depressive Disorder

The essential feature of Major Depressive Disorder is a clinical course by one or more Major Depressive Episodes (see below) without a history of Manic, Mixed, or Hypomanic Episodes. Episodes of Substance-Induced Mood Disorder (due to the direct physiological effect of a drug of abuse, a medication, or toxin exposure) or of Mood Disorder Due to a General Medical Condition do not count toward a diagnosis of Major Depressive Disorder. In addition, the episodes must not be better accounted for by Schizoaffective Disorder and are not superimposed on Schizophrenia, Schizophreniform Disorder, Delusional Disorder, or Psychotic Disorder.

The essential features of a major Depressive Episode is a period of at least 2 weeks (most of the day ,nearly every day) during which there is either depressed mood or the loss of interest or pleasure in nearly all activities. The episode must be accompanied by clinically significant distress or impairment in social, occupational, or other important areas of functioning. The individual must also experience at least four additional symptoms drawn from a list that includes:

- changes in appetite or weight, sleep and psychomotor activity
- depressed energy
- feelings of worthlessness or guilt
- difficulty thinking , concentrating, or making decisions
- recurrent thoughts of death or suicidal ideation, plans or attempts.

4.6.3 Substance abuse

A maladaptive pattern of substance use leading to clinically significant or distress, as manifested by one (or more) of the within a 12 month period: (1) recurrent use resulting in a failure to fulfill major obligations at work, school, or home; (2) recurrent use in situations which are physically

hazardous (e.g., driving while intoxicated); (3) recurrent substance-related legal problems resulting (e.g., arrests for substance –related disorderly conduct) or (4) continued use despite significant social or interpersonal problems caused or exacerbated by the effects of the substance (e.g., arguments with spouse about consequences of intoxication, physical fights) The symptoms do not meet the criteria for substance dependence for this class of substance.

Substance Dependence is a maladaptive pattern of substance use to clinically significant or distress, as manifested by three (or more) of the following, occurring at any time in the same 12 month period:

- (1) tolerance as defined by either of the following:
 - i. A need for markedly increased amounts of the substance to achieve intoxication or desired effect.
 - ii. Markedly diminished effect with continued use of the same amount of the substance
- (2) Withdrawal, as manifested by either of the following:
 - i. The characteristics withdrawal syndrome for the substance
 - ii. The same substance is taken to relieve or avoid withdrawal symptoms.
- (3) The substance is often taken in larger amounts or over a longer period than intended.
- (4) There is a persistent desire or unsuccessful efforts to cut down or control substance use.
- (5) A great deal of time is spent in activities necessary to obtain the substance , use the substance or recover from its effects
- (6) Important social, occupational, or recreational activities are given up or reduced because of substance use
- (7) The substance use is continued despite knowledge of having a persistent or recurrent physical or psychological problem that is likely to have been caused or exacerbated by the substance (e.g. continued drinking despite recognition that an ulcer was made worse by alcohol consumption)

4.6.4 Alcohol Abuse

Alcohol abuse requires fewer symptoms and, thus, may be less severe than Dependence and is only diagnosed once the absence of Dependence has been established. School and Job performance may suffer either from the aftereffects of drinking or from actual intoxication on the job or at school; child care or household responsibilities may be neglected; and alcohol related absences may occur from school or job. The person may use alcohol in physically hazardous circumstances. Legal difficulties may arise because of alcohol use. Finally, individuals with Alcohol Abuse may continue to consume alcohol despite the knowledge that continued consumption poses significant social or interpersonal problems for them. When these problems

are accompanied by evidence of tolerance, withdrawal, or compulsive behavior related to alcohol use, a diagnosis of Alcohol Dependence, rather than Alcohol abuse, should be considered. Since some symptoms of tolerance, withdrawal, or compulsive use can occur in individuals with Abuse but not dependence, one should determine if the full criteria for dependence are met.

4.6.5 Alcohol Dependence

Physiological dependence on alcohol is indicated by evidence of tolerance or symptoms of Withdrawal. Especially if associated with a history of withdrawal, physiological dependence is an indication of a more severe clinical course overall. (e.g. earlier onset, higher levels of intake, more alcohol –related problems) Withdrawal from alcohol can be unpleasant and intense; individuals with Alcohol dependence may continue to consume alcohol, despite adverse consequences, often to avoid or to relieve the symptoms of withdrawal. Some withdrawal symptoms, (e.g. sleep problems) can persist at lower intensities for months. Once a pattern of compulsive use develops, individuals with Dependence may devote substantial periods of time to obtaining and consuming alcoholic beverages. These individuals often continue to use alcohol, blackouts, liver disease, or other sequelae.

Note: Mental health diagnoses are made by psychiatrist, psychologist, or other mental health professionals who is specially trained to diagnose and treat mental illnesses. The mental health professional uses specially designed interview and assessment tools to evaluate a person for a mental illness. For the purposes of this study subjects with documented diagnosis according to the DSM IV, by a psychiatrist, psychologist or other mental health professional would be required to exclude a subject's with a history of Schizophrenia, Bipolar Disorder , Major Depressive Disorder , alcohol and/substance abuse.

4.7 Osteoporosis (Moses, 2012)

4.7.1 Dual X-ray absorptiometry (DXA)

DXA is a diagnostic test used to assess bone density. Dual-energy X-ray absorptiometry (DXA, previously DEXA) is a means of measuring bone mineral density (BMD). Two X-ray beams with different energy levels are aimed at the patient's bones. When soft tissue absorption is subtracted out, the BMD can be determined from the absorption of each beam by bone. Dual-energy X-ray absorptiometry is the most widely used and most thoroughly studied bone density measurement technology. The DXA scan is typically used to diagnose and follow osteoporosis

Upon completion of a DXA scan, the bone density of the patient is then compared to the average peak bone density of adults of same sex and race. This score is called the “T score and it expresses the bone density in terms of the number of standard deviations (SD) below peak young adult bone mass.

Note: Generally the DEXA Scan will have a reading from the spine, the hip and the forearm. The lowest most negative score should be used to qualify the subject for enrollment and enter into the EDC.

4.7.2 T-score

The World Health Organization has defined the following categories based on bone density in white women:

Normal bone	T-score greater than -1
Osteopenia	T-score between -1 and -2.5
Osteoporosis	T-score less than or equal to -2.5
Severe (established) osteoporosis	T-score less than -2.5 and 1+ osteoporotic fractures

Note: in this study a T-score of ≤ -2.5 is considered Osteoporosis and the subject is excluded.

4.7.3 Simple calculated osteoporosis risk estimation

The following risk assessments have been reported to appropriately identify women (SCORE) and men (MORES) who are likely to be at risk for osteoporosis.

Women: Simple Calculated Osteoporosis Risk Estimation (SCORE)

A risk assessment instrument, the “simple calculated osteoporosis risk estimation” (SCORE), has been reported to appropriately identify women likely to have low (t score ≤ -2 SD) bone mineral density (BMD) and who should be referred for bone densitometry. The majority of Osteoporosis risk is predicted by age, weight and ethnicity. The criteria for the SCORE questionnaire are as follows:

- a. Race not black : 5 points
- b. Rheumatoid Arthritis : 4 points
- c. Fracture after age 45 on wrist , hip or rib: 4 points per Fracture
- d. Age over 65; calculate 3 x (1st digit of age) Example for age 70 :21 points

- e. Weight: calculate $(-1 \times \text{weight in pounds})/10$. Example for weight 200 pounds: -20 point
- f. Estrogen therapy never use: 1 point

A result of 6 or above on the SCORE Questionnaire is associated with T-score below -2 SD. Osteoporosis testing with DEXA Scan is recommended if score of 6 or above. (Lydick 1998)

For Men: Male Osteoporosis Risk Estimation Score (MORES)

A risk assessment instrument, the “male osteoporosis risk estimation score” (MORES) has been reported to appropriately identify men who are likely to have low (t score ≤ -2 SD) BMD and who should be referred for bone densitometry. The majority of osteoporosis risk in males is predicted by age, weight, and a chronic obstructive pulmonary disease (COPD) diagnosis. The criteria for the MORES questionnaire are as follows:

- a. Age:
 - 1. 55 Years or younger (0 points)
 - 2. 56 to 74 years: 3 points
 - 3. 75 years or older: 4 points
- b. Confirmed COPD Diagnosis: 3 points
No COPD Diagnosis: 0 points
- c. Weight:
 - 1. 154 pounds or less: 6 points
 - 2. 155 to 176 pounds: 4 points
 - 3. Greater than 176 pounds (0 points)

A result of 6 or above on the MORES Questionnaire is associated with T-score below -2 SD. Osteoporosis testing with DEXA Scan is required if score of 6 or above. (Shepherd 2007)

5 Risk Analysis

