21. The subject has an active or chronic infection, either systemic or local.
22. The subject has Pathologic fractures of the affected shoulder
23. The subject has acute trauma of the affected shoulder
24. The subject has osteoporosis defined as a bone density T score of \leq -2.5. (A screening Questionnaire for osteoporosis, SCORE (Simple Calculated Osteoporosis Risk Estimation) and MORES (Male Osteoporosis Risk Estimation Score), will be used to screen patients who require a DEXA bone mineral density measurement.

Kellgren-Lawrence Scale

Osteoarthritis will be evaluated using the Kellgren-Lawrence Scale (Jacobson, 1996) as follows:

Grade of Osteoarthritis	Description
1	doubtful narrowing of joint space, possible osteophytic lipping
2	definite small osteophytes, possible narrowing of joint space
3	multiple moderately sized osteophytes definite joint narrowing, some sclerotic areas, possible deformation of bone ends
4	Large osteophytes, marked narrowing of joint space

Staging System of Cruess

Avascular Necrosis will be evaluated using the Staging System of Cruess (Cruess 1978)

Stage of Avascular Necrosis	Description
I	Documented only by magnetic resonance imaging or bone scan
II	Localized or mottled sclerosis, osteopenia
III	Crescent sign present, indicating a subchondral fracture
IV	Flattening and collapse of humeral head subchondral bone
V	Degenerative changes extending to glenoid side of joint

American College of Rheumatology

Rheumatoid Arthritis will be evaluated using the American College of Rheumatology (Aletaha 2010)

Joint Involvement (Choose option in each category)	Possible Points
1 large joint	0
2-10 large joints	1

1-3 small joints (with or without involvement of large joints)	2
4-10 small joints (with or without involvement of large joints)	3
> 10 joints (at least 1 small joint)	5

Serology (at least 1 test result is needed for classification)

Negative RF and negative ACPA	0
Low-positive RF or low-positive ACPA	2
High-positive RF or high-positive ACPA	3

Acute-phase reactants (at least 1 test result is needed for classification)

Normal CRP and normal ESR	0
Abnormal CRP or abnormal ESR	1

Duration of symptoms

< 6 weeks	0
≥ 6 weeks	1

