As with any foreign body implant, allergies and other reactions to device material may occur. Patients will be queried about allergies and previous implants; where material sensitivity is suspected, appropriate tests should be made to rule out sensitivity prior to implantation. The Eclipse Shoulder Prosthesis is manufactured from known materials such as Titanium and Cobalt Chrome and coated with Titanium plasma spray (TPS) and Calcium phosphate (CaP); the glenoid component is also manufactured from a known material, Ultra High Molecular Weight Polyethylene (UHMWPE). All of these materials have a long history of clinical use, including in similar medical devices. As the glenoid component is comprised of UHMWPE, there is no risk of metal-on-metal wear, which has recently been determined to cause long-term adverse biologic reactions with certain metal-on-metal hip prosthesis.

Loosening of the implant as a result of changed conditions in load transfer, fatigue wear disassociation of the components, or tissue reaction has been reported to occur (7% aseptic loosening of humeral head). Patients will be assessed for sufficient quantities or quality of humeral head and/or humeral neck bone stock prior to implant via radiograph. Loosening of the implant may also

be caused by inadequate anchoring technique. These risks are mitigated by assuring that the surgeons are properly trained on the specifics of the device, as well as the corresponding surgical procedure.

Specific surgeon training will help mitigate the risks of extreme weakening of the bone structure in the preparation the bone bed, unsuitable implant size selection, inadequate cleaning of the bone bed prior to implantation, excessive use of force in placing or anchoring the implant, creation splintering fractures, or development of bone tears. Additional training regarding the use of only the associated ArthroX delivery system, instruments, and trial prosthesis for implantation will mitigate the risks of dislocation, subluxation, and inadequate scope of movement as a result of failure to achieve optimum positioning of the implant. In addition, proper training on the surgical technique and the positioning of the implants will mitigate the risk of temporary or permanent nerve damage. Surgeon training on the implant utilize will be required of all surgeons in the study, and documentation of surgeon training will be recorded in the site binders (Appendix 2-3 Surgeon Training).

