6.2 Preoperative Evaluation: Visit 1 (-21 to day 0)

Once the subject has signed the informed consent and prior to surgery, they will have the following data collected and procedures conducted: (Appendix 2-5 Case Report Forms)

- Demographics /History CRF
 - Kellgren-Lawrence Scale
 - Staging System of Cruess
 - American College of Rheumatology
 - SCORE/MORES questionnaire
- Concomitant Medication & Therapy CRF (pain management only)
- Subject Report Survey's:

Note: Subject surveys are to be completed prior to the Physical, The survey should be QC'd for completeness, discrepancies, signed or initialed and dated, during the visit.

- SF36
- VAS
- Constant Score:
 - Subject will be asked to fill out the subject section regarding activities of daily living (sleep, work, recreation / sport).
 - Clinician completes objective section by assessing range of motion and strength
- Physical Exam/Shoulder Exam includes sensory and motor testing

- Radiograph(s)
- Note:
 - Serum or urine Pregnancy test if applicable
 - Enrollment Checklist
 - Patient Education regarding Total Shoulder Prosthesis, post-operative procedures and the follow-up study schedule.
 - Inform subjects that they will return post-op within 3 months, 6 months, 12 Months and 24 Months for follow-up.
 - Deviations
 - Note: Screening procedures may be done on different days within the screening window.

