
1 A Month =30 days
 
2 Informed Consent (ICF) is obtained and signed prior to any study related procedures and a revised ICF is signed at the next study visit prior to any new or revised study related procedures.
 
3 Medication /Therapy Form will document at least 3 months of conservative treatment as required per Inclusion Criteria
 
4 SF 36, VAS and Constant may be done during unscheduled visit only if one of the required time points was missed, must document in deviation log
 
5 The only Pre-op laboratory require for the study is a pregnancy test if female and with child bearing potential. Pregnancy test may be done at V1 and or V2.
 
6 Data for Enrollment is collected at screening and confirmed at Visit 2 prior to Randomization
 
7 Randomization will occur on visit 2 after Inclusion/Exclusion criteria is confirmed
 
8 Operative detail is collected at Visit 2
 
9 Adverse Events are collected after subject has received treatment
 
10 All Radiographs must be done as per Radiographic Protocol inadequate Radiographs should be repeated within the time point window.
 
11 Radiographs must be available in medical record to validate Inclusion/Exclusion Criteria, if ordered during screening and results available to confirm eligibility prior to Randomization
 
12 The post-operative Radiographs must be done per Radiographic protocol and within 72 hours of surgery.
 
13 The Rehabilitation Plan is initiated on the evening of surgery –Refer to Appendix 2-2
 
14 If subject terminates prior to 24 months all end of study procedure and form are completed as if the subject completed 24 months.
								

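### Section 4.7.3 only recommends for women the DEXA scan that exclusion 24 treats as required, so a flagged woman could be randomised without the T-score that decides the exclusion

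*Combined protocol and SAP*

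**What the plan says.** Exclusion 24 appears in the Protocol Summary (section 1) and in section 4.2.2. It bars a T-score of -2.5 or lower and says that SCORE and MORES "will be used to screen patients who require a DEXA bone mineral density measurement". Both questionnaires are named together, and neither has a cut-off there.

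The cut-off is given only in section 4.7.3, where it is 6 or above for each questionnaire. For women the text reads "Osteoporosis testing with DEXA Scan is recommended if score of 6 or above". For men it reads "Osteoporosis testing with DEXA Scan is required if score of 6 or above".

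The result of the scan decides eligibility. Section 4.7.2 says that a T-score at or below -2.5 "is considered Osteoporosis and the subject is excluded". Section 4.7.1 deals with several readings from one scan: "The lowest most negative score should be used to qualify the subject for enrollment", with that value entered in the EDC.

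The Visit 1 list in section 6.2 contains the "SCORE/MORES questionnaire" but no DEXA. The Schedule of Events (Appendix 2-4) names SCORE and has no DEXA row. Its footnotes place randomisation after eligibility is confirmed at Visit 2.

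**The concern.** One scan has two rules. Exclusion 24 treats the scan as something a flagged patient must have, whichever questionnaire raised the flag. Section 4.7.3, which a site must consult to learn who is flagged, makes it mandatory for men and advisory for women. Two sites could each believe they were following the protocol and handle the same woman differently.

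The main stake is safety. Eclipse has no stem; section 7.3 describes a trunion held in the proximal humerus by a hollow screw. Section 9.1.3 includes fracture due to weakened bone among the events that may be device-related, and section 5.1 counts the selection criteria among the measures that limit risk. Osteoporosis is an exclusion the plan chose for itself. If the scan is skipped in a flagged woman, that exclusion is not applied to her.

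**Working it through.** No sample size, power or alpha figure in the plan depends on this point, so there is none to reproduce. The check is a comparison of texts, followed by simple arithmetic on who is flagged.

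**1. The two rules side by side**

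| | Women (SCORE) | Men (MORES) |
|---|---|---|
| Exclusion 24 | scan required, no cut-off | scan required, no cut-off |
| 4.7.3, cut-off | 6 or above | 6 or above |
| 4.7.3, stated association of a positive result | T-score below -2 SD | T-score below -2 SD |
| 4.7.3, status of the scan | recommended | required |

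The cut-off and the stated association are the same, and the plan gives no reason for treating the sexes differently. A flag points to a T-score below -2, whereas exclusion needs -2.5 or lower. The questionnaire therefore cannot stand in for the scan.

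**2. Does other text order the scan for a flagged woman?**

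- Section 4.7.1 says which T-score to use once a scan exists. It does not order one.
- Section 6.2 and the Schedule of Events list the questionnaire but no scan.
- A schedule footnote says "Radiographs must be available in medical record to validate Inclusion/Exclusion Criteria". No matching footnote covers a T-score.
- Section 6.3 has the enrollment checklist reviewed before randomisation, and section 8.10 has eligibility data verified against source. Neither, as described, says that a T-score must exist.
- Section 5.1 says "Patients will be assessed for sufficient quantities or quality of humeral head and/or humeral neck bone stock prior to implant via radiograph". Exclusion 3 and the indication in 2.3.1 also address bone quality or bone stock. None of these yields a T-score.

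None of the available text settles the matter.

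**3. Who is flagged under the plan's own formula**

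Inputs from 4.7.3: 5 points if not black; 4 for rheumatoid arthritis; 4 per qualifying fracture; over age 65, 3 × the first digit of age; minus weight in pounds / 10; 1 if oestrogen was never used.

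For a non-black woman over 65 with no rheumatoid arthritis or qualifying fracture, who has used oestrogen, with first age digit d and weight w:

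5 + 3d − w/10 ≥ 6, so w ≤ 10 × (3d − 1)

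If she never used oestrogen: 6 + 3d − w/10 ≥ 6, so w ≤ 10 × 3d

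| Age | Oestrogen used | Never used |
|---|---|---|
| 66–69 (d = 6) | ≤ 170 lb | ≤ 180 lb |
| 70–79 (d = 7) | ≤ 200 lb | ≤ 210 lb |
| 80–89 (d = 8) | ≤ 230 lb | ≤ 240 lb |

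For black women each limit is 50 lb lower (150 and 160 lb in their 70s). Rheumatoid arthritis or a fracture raises it by 40 lb each. At 65 or younger, without either, the score is at most 5 + 1 − w/10, which is below 6 at any weight, so no one is flagged.

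**4. One concrete pair**

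Take two patients aged 72 and weighing 170 lb. A man without COPD scores 3 + 4 = 7 on MORES, and his scan is required. A non-black woman who has used oestrogen scores 5 + 21 − 17 = 9 on SCORE, and hers is recommended.

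**The case against.** The strongest reply is that the binding rule is clear. Exclusion 24 is an eligibility criterion, section 4.2 makes every criterion mandatory, and the criterion names both questionnaires as identifying patients who need the scan. The advisory sentence sits in a description of a published instrument and may simply carry over the language of its source. On that reading a careful site scans every flagged woman. The enrollment checklist and the case report forms (Appendix 2-5) are not in the available text and may already demand a T-score. All of this stands, and it makes exclusion 24 the stronger reading. It does not remove the conflict, because exclusion 24 has no cut-off and the section that supplies one softens the rule for women.

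The missing DEXA line in the schedule is also weaker evidence than it looks. It is missing for men too, whose scan is plainly mandatory. The omission fails to resolve the conflict, but it does not show that the women's scan is optional.

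A reader might try to size the problem. Section 5.1 gives 61.3% women and 54.6% + 14.7% = 69.3% aged 65 or over among past US procedures. Multiplying gives 0.613 × 0.693 = 42.5%, or about 125 of the 294 evaluable patients. That product assumes age and sex are independent, and its base includes 10.3% fracture cases. Going further needs the weight distribution, the share already scanned and the share with a T-score of -2.5 or lower, and the documents give none of these.

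A reader might also infer a threat to the primary test: section 4.1.2 sets no time limit on finding an eligibility violation, so a scan prompted by a failure could remove that patient from the Per Protocol set. That needs a postoperative DEXA, which the plan does not schedule, ordered selectively after failures. Nothing in the documents says this would happen.

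**Conclusion.** The inconsistency is real and should be corrected. A site that follows 4.7.3 as written could randomise a woman with SCORE of 6 or above without the measurement that decides a stated exclusion, and the available text does not prevent it. This is a possibility, not a demonstrated practice: it depends on a site preferring the weaker wording and on the checklist and forms not closing the gap.

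The consequence is mainly for safety and for consistent eligibility across sites. By the plan's formula the flag reaches non-black women in their 70s weighing up to 200 lb, or 210 lb without past oestrogen use, so it is not confined to very light patients. How many women would go unscanned, and how many of those would have osteoporosis, cannot be computed from the documents. No effect on sample size, power or type I error is shown.

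**What to change.** 1. In the SCORE paragraph of 4.7.3, change *recommended* to *required*.
2. In exclusion 24 (sections 1 and 4.2.2), state the cut-off of 6 or above for both questionnaires.
3. Add *DEXA if SCORE or MORES is 6 or above* to the Visit 1 list in 6.2 and to the Schedule of Events, with a footnote that no flagged patient is randomised without a T-score in the EDC.

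The cost is one DEXA for each flagged woman not already scanned, which exclusion 24 already implies, and some additional screen failures. The planned sample size and the follow-up visits are unchanged.

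If women have already been randomised, a count by arm of those with SCORE of 6 or above and no T-score would be informative but is optional. I would not restrict 4.1.2 to T-scores recorded before randomisation. A pre-surgery scan found later in the records could then leave a woman with documented osteoporosis in a Per Protocol set meant to match the labelled population.
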